## **STUDY GROUPS:**

After participants complete the baseline survey, they will be randomized to either the control group (usual ED care with discharge instructions relevant to the child's diagnosis and a study handout) or the TCBD intervention group (an ED counseling session plus eHealth after ED discharge). Please also refer to section 3. D.1. for a complete outline of the study details for each group over the course of the study.

Main differences between intervention and control include the following:

### **At baseline visit (enrollment in study):**

1) Control group -- after taking the baseline survey, they will be given a study handout that summarizes the IL law on child passenger safety and provides a few online resources for parents on child passenger safety.

# Emergency Medicine Prospective Protocol

2) TCBD Intervention group --after taking the baseline survey, they will receive a brief motivational interviewing inspired counseling session with the research coordinator in addition to the same study handout sheet that the control group will receive. During the MI counseling session, participants will talk to the RC about how their child normally rides in their car, their goals for traveling safely with their child, and how they might reach these goals. Additionally, the intervention group will receive direct access to the study's mobile friendly website "site," Car Seat Compass. The site will provide parents with custom feedback based on their answers within the baseline survey regarding how their child normally rides in their vehicle and their general child passenger safety practices with that child. The site will give them answers to common questions about traveling with children as well. The control group will not have access to this site throughout the study. However, the control group will obtain access to the study website after the conclusion of their 12 month follow-up.

Both groups will participant in all of the Tiny Cargo check-ins and the 6- and 12 month follow up visits scheduled over the course of the study. Those elements of the study do not change based on the group someone is enrolled in.

## Monthly Photo Requests:

Both groups will be asked to send the study team photos of how their child normally rides in their vehicle and will be paid the same incentive amounts. However, if major misuse or errors are visible within the photos that participants submit, then the text messages sent to participants will vary slightly depending on which group you are enrolled in.

- 1) control group --they will receive a concise text message for any major misuse/errors that are visible and how to adjust for it. Non-critical errors will not elicit a direct text message response from the study team.
- 2) TCBD intervention group --they will receive a slightly longer text message that is framed within the spirit of motivational interviewing that addresses the major misuse/error and possible solutions to adjust for it. They will also receive tailored messages for any non-critical misuse/errors.

\*\* See section 9 (Supporting documents) of the IRB application for an excel file that serves as a library of text messages that will be provided to participants when major misuse/errors are visible (in-person or via photos) based on the study group they are enrolled in. This is a sample of the messages that will be used and sent out, but not meant to be a comprehensive library of messages. The RC will use their discretion when reviewing misuse/errors and adjusting messages as needed.

## Study Text Messages:

Both groups will receive study text messages from the study team over the course of their enrollment in the study. However, the TCBD intervention group will receive tailored text messages each month on top of the basic reminders for follow-up visits and feedback related to the photos they submit each month.

The tailored text messages that will be sent to the TCBD intervention group will be custom tips and info based on the participants answers to study surveys and the type of child restraint system they are recommended to be using. \*\*Please see section 9 of the application to view a document called, TCBD library and error messages and refer to the sheet labeled, "general message library." The text messages included within this sheet will be used to support the intervention group over the course of the study.

# Emergency Medicine Prospective Protocol

## After the 6-month follow-up assessment:

Participants in the intervention group only who continue sub-optimal child restraint system use (not using the recommended seat) will be re-randomized to one of two groups:

- 2) TCBD basic intervention group
- 3) TCBD enhanced intervention group

The enhanced TCBD intervention group will include one additional motivational interviewing (MI) session by phone in Month 7/8 and one to two additional tailored text messages in Months 7-12 (total of 7 tailored tips during these months compared to 4 tailored tips for those in the basic TCBD). The extra text messages will be sent to those in the enhanced TCBD group until size-appropriate restraint use is observed. Caregivers receiving enhanced TCBD will be encouraged to obtain a free seat check with a certified child passenger safety technician (CPST) in the community.

The basic TCBD intervention group will continue on in study without any changes.

## **3.3 Study Measures**

Over the course of this study, participants will complete the following surveys: screen, baseline, 6- and 12-month survey. At the 6-month follow-up, the participants will also complete a brief health literacy assessment called the Newest Vital Sign.

The selected measures for the surveys are reliable, valid, and have been pilot tested in the study population. Measures will be assessed at screening, baseline and re-assessed at the 6- and 12-month follow-up visits. Assessments will be self-administered or RC facilitated on a study iPad in the ED and at in-person follow-up assessments (Months 6 and 12). Skip patterns will reduce administration time. Our team has found baseline assessment lasting 20 minutes to be feasible and acceptable to caregivers in the ED setting during pilot testing.

Table 1 illustrates survey measures for this study along with the frequency/timing of assessments.

Table 1: Measures	Assessment Month(s)
OUTCOMES	
Primary Outcome	
Size Appropriate Restraint Use (dichotomous)	6 and 12
Child Passenger Safety Score direct observation	6 and 12
Secondary Outcome	
Child Passenger Safety Score remote observation	ED/Baseline through 12
Exploratory Cost Measures	
Intervention Time (ED, Phone MI) for RA/Counselor	ED/Baseline and 2
Intervention Time (ED, Phone MI, texts, web app) for caregiver	ED/Baseline through 12
Material Costs - iPads, computers, maintenance	ED/Baseline through 12
Intervention Costs - Photograph review, texts, web app	ED/Baseline through 12
MODERATORS/MEDIATORS	
Caregiver Demographic Characteristics, reason for ED visit	ED/Baseline
Child Size	

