# Emergency Medicine Prospective Protocol

person (e.g., they move out of state), they may also send us photos of their child as they usually ride in their car via text message or via a video chat (e.g., Facetime or google hangout).

- **\*\*See section 9 of IRB app, "supporting documents" for a document called, "TCBD text library and error messages" and refer to the sheet labeled, "Response to errors."** This document provides scripted responses that the RA will use when major misuse and/or errors are visible during the Tiny Cargo check-ins. The TCBD intervention messages are referred to as "Scripted MI response" while the control group's responses are referred to as "scripted control response."
- After the 6-month follow-up assessment, caregivers in the intervention group only who continue suboptimal CRS use will be re-randomized to receive either the basic or enhanced intervention.
- The enhanced TCBD intervention group will include one additional motivational interviewing (MI) session by phone in Month 7/8 and one to two additional tailored text messages in Months 7-12 (total of 7 tailored tips during these months compared to 4 tailored tips for those in the basic TCBD). The extra text messages will be sent to those in the enhanced TCBD group until size-appropriate restraint use is observed. Caregivers receiving enhanced TCBD will be encouraged to obtain a free seat check with a certified child passenger safety technician (CPST) in the community.
- The basic TCBD intervention group will continue on in study without any changes.

**Study Phase:** Phone Counseling Session --Month 7/8

**Study Group:** Enhanced TCBD Intervention Group

**Setting:** In-person or remote

**Timing:** Within 1 month

Phone counseling session (enhanced TCBD intervention):

After the study subject completes their 6-month follow-up visit, the study team will determine if the child is using the recommended child restraint system (car seat or booster seat) for their age and size. The intervention group subjects whose children are NOT using the recommended restraint will be randomly assigned (like flipping a coin) to one of two groups. They cannot pick the group they will be in.

The groups are:

- Group 2 (basic TCBD): They will keep taking part in the study with the basic intervention and nothing will change.

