- Group 3 (enhanced TCBD): They will keep taking part in the intervention arm of the study but will be asked to talk with a Car Seat Coach (i.e., a behavioral research assistant trained for the study) by phone for about 20 minutes. The phone call will cover some of the challenges and successes they are having with traveling safely with their child. They will also get 1 or 2 additional study text messages each month. These extra text messages will include:
  - Feedback related to the photos they send us of their child riding in their car
  - Feedback related to survey answers

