
# Emergency Medicine Prospective Protocol

trajectory types in 100% of replications, and the mean trajectories in those four groups were characterized correctly.

**Exploratory Aim:** Aligning with the NIH guidance on health economics research, we plan a cost analysis of the intervention to inform wider dissemination and implementation in settings outside of the ED. Unmeasured time costs for staff or for participants can be a key barrier to the implementation and long-term viability of a new intervention since preventive and screening recommendations can compete for implementation time from staff. We will address this potential barrier by measuring all relevant costs associated with the study interventions through primary data collection. We will measure the total costs of the intervention from participant and health system perspectives by gathering estimates of intervention resource requirements, including personnel costs, implementation time, participant time, and material costs. Resource costs will include intervention development, training, and implementation. All costs will be adjusted to US 2017 dollars using the Gross Domestic Product Price Index. Control costs will be adjusted to reflect the proportion of time study participants spend on the app. We will calculate costs of the intervention per child. Net costs (savings) will be calculated by subtracting mean costs per participant in the control condition from mean costs per participant who receive the basic TCBD and the enhanced TCBD interventions. Given typical skewness, we will report means, medians, standard errors, minimum, maximum, and quantiles to provide information on cost measures. Tests will be employed to assess distributions of cost measures and identify appropriate methods for generating confidence intervals, such as non-parametric bootstrapping. We will also estimate cost-effectiveness as measured by dollars per caregiver using a size-appropriate CRS and using the CRS correctly. Economic data will provide key information about the relative costs and benefits associated with the intervention, inform scalability, and help prioritize future implementation strategies in EDs and other settings that serve young children (e.g., doctor's offices, schools).

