The CPaSS electronic survey tool will be used by research assistants to observe and record assessment scores for the Tiny Cargo check-ins each month that a participant is enrolled in the study. The CPaSS tool will be used either in direct observation with a family or via photos submitted electronically via text message to the study team.

CPaSS observations recorded from review of the digital photographs will be collected in surveys on the Northwestern University portal to the Qualtrics survey platform that contain study-specific codes only. Qualtrics will house the data for the CPaSS assessments and will only use a subject identifier (ID number) to connect the participant's data with their information. No unique identifying information will be collected within this assessment tool. When it is exported from Qualtrics, the data will be saved to a secure folder on the LCH secure network.

5) Audio recordings of the MI counseling sessions (conducted at the baseline visit, and/or Month 7/8 via phone)

Although the focus of this study is not on child abuse, because of the nature of the study, caregivers may disclose information that raises concerns for potential child abuse or neglect during the MI counseling sessions (baseline visit and/or phone session). The consent form will contain a statement regarding the mandatory reporting requirements. Staff training will include review of the study protocol regarding the limits of confidentiality, liaison with ED staff (i.e., clinical

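### Table 1 collects counsellor time at baseline and Month 2, but the enhanced group's phone session is in Month 7/8, so its staff time has no scheduled collection point

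*Combined protocol and SAP*

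**What the plan says.** Table 1 (section 3.3) has four exploratory cost rows. The row for staff time, "Intervention Time (ED, Phone MI) for RA/Counselor", is to be assessed at "ED/Baseline and 2". The other three rows (caregiver time, material costs, intervention costs) run from baseline through Month 12.

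The phone session is dated in several places:

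- Section 3, under the follow-up visits, gives the enhanced group "one additional motivational interviewing (MI) session by phone in Month 7/8". Section 3.2 and the text on what follows the 6-month assessment say the same, and section 3.1 gives the same month.
- The study-phase heading in section 3 is "Phone Counseling Session --Month 7/8", for the enhanced group only. The caregiver talks with the coach "by phone for about 20 minutes".
- Section 8.2, item 5, lists the recorded counselling sessions as "conducted at the baseline visit, and/or Month 7/8 via phone".

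Section 2 mentions a booster session by phone without giving a month.

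On costs, section 2.2 and the Exploratory Aim in section 6.1 plan net costs against control for basic and enhanced TCBD, with personnel costs and implementation time included. Section 6.1 undertakes to do this by "measuring all relevant costs associated with the study interventions through primary data collection".

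**The concern.** The row names the phone session, so its time is meant to be captured. Month 2 cannot be the month of the enhanced group's session, because caregivers enter that group only by re-randomization after the 6-month visit. Staff who follow the table would log time at baseline, find no session to log in Month 2, and have no scheduled point in Month 7/8.

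The phone session is the main item of staff counselling time that distinguishes enhanced from basic TCBD. If its minutes are not logged, the error runs one way: the personnel cost of enhanced TCBD comes out too low relative to basic. Section 6.1 itself gives unmeasured staff time as a possible barrier to adoption, so this is a cost that the analysis sets out to measure. Staff time that is not logged when the session happens is hard to rebuild later.

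**Working it through.** The plan states no figure for this cost, so there is none to reproduce. The check has two parts.

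**1. Timing, side by side**

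| Item | Month stated | Where |
|---|---|---|
| Counsellor time, ED and phone sessions | Baseline and 2 | Table 1, section 3.3 |
| Caregiver time, including phone session | Baseline through 12 | Table 1, section 3.3 |
| Delivery of the enhanced phone session | 7/8 | Sections 3, 3.1, 3.2; text on the period after the 6-month assessment |
| Recorded counselling sessions | Baseline and/or 7/8 | Section 8.2, item 5 |
| Any counselling session in Month 2 | None described | Whole protocol |

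The Month 2 entry matches no session, and the Month 7/8 session matches no entry in the counsellor row.

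**2. Size of the uncollected time**

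Inputs:

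- 516 TCBD caregivers available for analysis, with 75% of TCBD caregivers re-randomized (section 6.1)
- 1:1 re-randomization (section 3.2)
- about 20 minutes per call (section 3)

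Calculation:

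- Re-randomized: 516 × 0.75 = 387.
- Allocated to enhanced: 387 / 2 = 193.5, about 193.
- Counsellor time: 193.5 × 20 min = 3,870 min; 3,870 / 60 = 64.5 hours.

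Without the 80% attrition correction, starting from 900 enrolled (section 4.2):

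- At the 516:204 split: 900 × 516/720 = 645 TCBD; 645 × 0.75 / 2 = 241.9 enhanced; × 20/60 = 80.6 hours.
- At the 3:1 ratio of section 3.2: 900 × 0.75 = 675 TCBD; 675 × 0.75 / 2 = 253.1 enhanced; × 20/60 = 84.4 hours.

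**Check that about 193 is the group size the plan had in mind.** Section 6.1 claims 80% power for enhanced against control at a standardized difference of 0.28. With 204 and 193 caregivers, 0.28 × √(204 × 193 / 397) = 0.28 × 9.96 = 2.79. Then 2.79 − 1.96 = 0.83, which gives 79.6% power, in line with the stated 80%.

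**Share of scheduled session minutes.** Section 3 gives about 20 minutes of counselling at baseline and about 10 minutes for showing the website. The call is then 20 / (20 + 20) = 50% of counselling minutes, or 20 / (20 + 20 + 10) = 40% if the demonstration counts as staff time. These are shares of minutes, not of cost.

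**The case against.** The case against giving this weight has four parts.

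- **The caregiver row nearly covers it.** That row names the phone session and runs through Month 12. The call is one caregiver with one coach, so the caregiver's minutes approximate the counsellor's minutes on the line. This stands as a possible substitute. It does not cover preparation or documentation, and the plan nowhere says that caregiver minutes will stand in for staff minutes.
- **The general commitment and the recordings cover it.** Section 6.1 promises to measure all relevant costs, and consented sessions are audio recorded. The promise sets no collection time. Under section 8.2 the recordings are made for fidelity and destroyed once fidelity monitoring is completed, and no use for costing is planned. Recovery is possible but not provided for.
- **The entry may be a slip.** Every other Table 1 cell with more than one time point ends in 12, so a dropped digit cannot be excluded. The documents do not say. Either way, the cell as it stands needs correcting.
- **The session may not be the only one by phone.** Section 3 allows the baseline session in person or over the phone, and section 4.5 has remote recruits complete the enrolment-phase procedures by phone. This stands. A reader might infer from Table 1 that counsellor time on the phone would be recorded as zero for everyone. That does not follow, because baseline sessions held by phone fall under the baseline entry.

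**Conclusion.** The inconsistency is real, and it is confined to one cell of a data-collection schedule. As written, counsellor time for the enhanced group's Month 7/8 call has no collection point, and the exploratory personnel cost of enhanced TCBD could be understated relative to basic. The amount is about 20 minutes per enhanced caregiver, or about 65 hours in total (81 to 84 hours without the attrition correction). These totals assume the plan's re-randomization rate, equal allocation, and that every enhanced caregiver completes a call of about 20 minutes.

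Two stronger conclusions are tempting and not supported. One is that half of the enhanced group's counsellor cost would be lost: the share of minutes is 40% once the website demonstration is counted, and a share of minutes is not a share of cost. The other is that enhanced TCBD would look almost as cheap as basic: the documents give no unit costs, and texts, photograph review, web app and materials are costed through Month 12 in other rows. Nor is it certain that the time would be lost, since staff could log it despite the table.

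The point is minor. It touches no primary or secondary outcome, and no randomization or power statement.

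**What to change.** Reconcile the counsellor-time cell in Table 1 with the text that dates the phone session, so that the row covers the month in which the session is delivered. Either ED/Baseline and 7/8, or ED/Baseline through 12 to match the other cost rows, would do this. If the Month 2 entry was meant for something else, say what it is and keep it as a separate time point.

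The cost is one table cell and, if staff time is logged on a form, the matching time point on that form. Nothing in the intervention, its timing or the efficacy analysis changes. It is best done before Month 7/8 calls take place. For any calls already made without a log, the cost report should say how counsellor minutes were obtained.

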# Emergency Medicine Prospective Protocol

Measured weight and length/height	ED, 6, and 12
Self-Determination Theory Constructs	
Treatment Self-Regulation Questionnaire 	ED/Baseline, 6, and 12
Confident rulers and Perceived Competence Scale 	ED/Baseline, 6, and 12
Health Care Climate Questionnaire 	12 months
Health Literacy and Numeracy	
The Newest Vital Sign 	6 months
Caregiver Emotional State, Stress, Coping	
State-Trait Anxiety Inventory 	ED/Baseline
Risk Behavior Diagnosis Scale 	ED/Baseline
Parenting stress index	ED/Baseline
Marlowe-Crowne Social Desirability Scale 	6 months
Child Passenger Safety Hassles Scale 	ED/Baseline, 6, and 12

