## **2.2 Secondary Objectives**

Additionally, we will determine moderators (caregiver sex, race, child age) and mediators (Self-Determination Theory constructs of autonomy, relatedness, competence; emotional state at ED recruitment) of the intervention effects at 12-month follow-up.

Finally, we plan a cost analysis of the intervention to inform wider dissemination and implementation in settings outside of the ED. We will measure the total costs of the intervention from participant and health system perspectives by gathering estimates of intervention resource requirements, including personnel costs, implementation time, participant time, and material costs. We will calculate costs of the intervention per child. Net costs (savings) will be calculated by subtracting mean costs per participant in the control condition from mean costs per participant who receive the basic TCBD and the enhanced TCBD interventions. We will also estimate cost-effectiveness as measured by dollars per caregiver using a size-appropriate CRS and using the CRS correctly

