## 3.4 Study Endpoints

### 3.4.1 Primary Study Endpoint

The primary outcomes (size-appropriate CRS use and CPaSS) will be assessed in-person at Month 12. The secondary outcome, the CPaSS trajectory, is a measure of correct and consistent restraint use in response to the intervention and will be assessed by scoring photographs submitted by caregivers (Months 1-5; 7-11) and collected by the study team (Months 6 and 12). Photographs will be scored using the CPaSS tool by research team members blinded to the treatment group.

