**SubAim:** We will determine moderators (caregiver sex, race, child age) of the intervention effects and mediators (Self-Determination Theory constructs of autonomy, relatedness, competence; emotional state at ED recruitment). We hypothesize that disparities in CRS use can be reduced through a tailored intervention that increases autonomous motivation, competence, and relatedness for correct CRS use. **Statistical Analysis:** **Moderation:** Within the GLM(M) modeling framework described above, we will evaluate moderation by including interactions between treatment group and sex-, race-, and age-based groupings. We will test whether sex as a biologic variable modifies the intervention effect, but will be underpowered to detect differences because children are infrequently with a male caregiver when seeking emergency care (10-15% in our pilot data). **Mediation:** We will use Imai's counterfactual mediation method, a very general framework that takes models for the outcome and mediator as inputs, to estimate mediation effects. Traditional mediation analysis can be susceptible to bias due to model misspecification and design limitations and limitations in the classes of statistical models, that can be accommodated (typically linear regressions for both the mediator and outcome) but the Imai framework can accommodate a wide variety of distributions for both the mediator and the outcome; our initial specification will be a logistic model for the binary variables and a linear (Gaussian) model for the numeric variables. We will use a quasi-Bayesian approach to draw from conditional distribution of the mediator given the "treatment" and other covariates, and that of the outcome given the exposure, mediator, and other covariates, to construct hypothesis tests for the proportion mediated; this approach is robustly implemented in the R package mediation.

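### The Health Care Climate Questionnaire is scheduled only at Month 12, alongside the outcome it would explain, so its planned mediation result cannot be told from reverse causation

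*Combined protocol and SAP*

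**What the plan says.** Section 2.2 sets out to determine "mediators (Self-Determination Theory constructs of autonomy, relatedness, competence; emotional state at ED recruitment) of the intervention effects at 12-month follow-up". Section 6.2 (SubAim) repeats the constructs and hypothesises that disparities can be reduced by an intervention that "increases autonomous motivation, competence, and relatedness for correct CRS use".

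Table 1 in section 3.3 has a block for moderators and mediators. Under its sub-heading "Self-Determination Theory Constructs" stand three rows:

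- the Treatment Self-Regulation Questionnaire: baseline, Month 6 and Month 12;
- "Confident rulers and Perceived Competence Scale": baseline, Month 6 and Month 12;
- "Health Care Climate Questionnaire" (HCCQ): Month 12 only.

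The text introducing Table 1 says in general terms that measures are repeated at both follow-up visits, which does not match the HCCQ row.

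On outcome timing, section 3.4.1 states: "The primary outcomes (size-appropriate CRS use and CPaSS) will be assessed in-person at Month 12". Table 1 and section 3.2 also list Month 6.

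On method, section 6.2 states: "We will use Imai's counterfactual mediation method, a very general framework that takes models for the outcome and mediator as inputs, to estimate mediation effects". Hypothesis tests for the proportion mediated follow. Section 6.2 does not say which time point of each mediator is used. It describes no lagged model, no adjustment for Month-6 behaviour and no sensitivity analysis.

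**The concern.** A mediator should come before the outcome it explains. The HCCQ, as scheduled, does not: it is collected at the Month-12 follow-up, where restraint use is also observed. For the Month-6 outcome it comes after the event.

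Reverse causation is plausible in this design. Restraint use at Month 6 decides which intervention caregivers can be re-randomised to an extra counselling session. The extra texts in the enhanced arm stop once appropriate restraint use is seen (section 3.2). Feedback texts depend on visible misuse. Behaviour therefore shapes the contact that a climate scale might reflect, and a caregiver who ended up with the right restraint may also simply rate that contact more kindly.

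At stake is the explanatory claim, not efficacy. A test of the proportion mediated could credit the HCCQ with a mechanism that the data cannot establish.

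**Working it through.** The plan gives no power or size figure for mediation, so there is nothing to reproduce. The finding rests on time order; the arithmetic shows how large the artefact could be.

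**Inputs from the documents.** HCCQ at Month 12 only (Table 1). Outcome at Month 12 (section 3.4.1). From section 6.1: 204 controls and 516 TCBD analysed, a standardised difference of 0.25 for CPaSS, and response rates of 17% and 27.6%.

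**Assumptions.** Pure reverse causation: treatment T changes behaviour Y, Y changes the HCCQ score M, and T has no other effect on M. Residual variance of M is 1. The reverse effect b is 0.3, 0.5 or 0.8. The method is linear product of coefficients, a simplification of the planned one (a linear probability model for the binary outcome). The true mediated share is zero throughout.

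**1. Formula.** The effect of T on M is b × (effect of T on Y). With v the within-arm variance of Y, the slope of Y on M given T is b × v / (b² × v + 1). Multiplying the two and dividing by the total effect gives

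share = b² × v / (b² × v + 1),

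which is the squared within-arm correlation.

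**2. CPaSS** (v = 1).
- b = 0.3: 0.09 / 1.09 = 8%
- b = 0.5: 0.25 / 1.25 = 20%
- b = 0.8: 0.64 / 1.64 = 39%

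Simulation (4,000 trials each) gave 8.1%, 20.1% and 39.4%. Both paths were significant in 13%, 28% and 49% of trials.

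**3. Binary restraint use.** Within-arm variances are 0.17 × 0.83 = 0.1411 and 0.276 × 0.724 = 0.1998. Weighted by arm size, v = (204 × 0.1411 + 516 × 0.1998) / 720 = 0.183.
- b = 0.3: 0.0165 / 1.0165 = 1.6%
- b = 0.5: 0.0458 / 1.0458 = 4.4%
- b = 0.8: 0.1172 / 1.1172 = 10.5%

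Simulation gave 1.5%, 4.5% and 10.6%, with both paths significant in 6%, 10% and 16% of trials. The shares are smaller because the same shift in HCCQ score between users and non-users is a weaker correlation.

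**4. Can Month-12 data alone decide?** Take CPaSS with b = 0.5. Given T, var(M) = 0.25 + 1 = 1.25 and cov(M, Y) = 0.5. A forward model with T to M = 0.5 × 0.25 = 0.125, M to Y = 0.5 / 1.25 = 0.40, direct effect 0.25 − 0.40 × 0.125 = 0.20 and residual variance 1 − 0.25 / 1.25 = 0.80 has exactly the same joint distribution. It implies 0.125 × 0.40 / 0.25 = 20% mediated, where the reverse model implies none. No analysis of Month-12 data alone, and no larger sample, separates them.

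**5. What a Month-6 value would do** (CPaSS, b = 0.5). Let rho be the within-arm correlation of Month-6 and Month-12 behaviour (assumed 0.3, 0.5, 0.7). The slope of Month-12 Y on Month-6 M is 0.5 × rho / 1.25 = 0.4 × rho, so the share is 0.125 × 0.4 × rho / 0.25 = 0.2 × rho: 6%, 10% and 14% (simulated 5.8%, 9.8%, 13.7%). Adjusting also for Month-6 behaviour gave 0% at each rho, because under these assumptions T is unrelated to Month-6 M once Month-6 behaviour is known.

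**The case against.** **Survey before check-in.** The Month-12 survey may be completed ahead of the observation (section 3, follow-up visits; section 5.1.4). This does not restore time order: the check-in records how the child usually rides, which can predate the survey.

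**A climate scale needs prior contact.** This is a fair reason to have no baseline value. It does not rule out Month 6, when both arms have had months of texts and photo feedback.

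**A Month-6 mediator misses the enhanced component.** This stands. Re-randomisation follows the Month-6 assessment, and the extra session and texts come later. It is a reason not to move all three scales to Month 6.

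**Relatedness.** A reader might infer that the relatedness hypothesis itself rests on an unusable measure. The documents do not say which instrument measures which construct. Three constructs and three rows suggest that the HCCQ stands for relatedness, but the title of the reference cited for it (no. 162) concerns autonomy support. Nor does a place in a mixed moderator/mediator block prove that each row enters the mediation model, although this row sits under the constructs that section 2.2 names as mediators.

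**Size.** A reader might also take the CPaSS shares to hold for restraint use, or suppose that a false mediation finding is near certain. Neither is supported. The binary shares are much smaller, and in most simulated trials the two paths were not both significant.

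**Conclusion.** The point holds for the HCCQ. As scheduled, it shares its only time point with the outcome, and the planned test cannot tell mediation from reverse causation. If the HCCQ is the relatedness measure, relatedness has no mediator value before Month 12.

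The percentages in the working illustrate size only. They depend on assumed reverse effects, linear models and a true mediated share of zero. The conclusion rests on the schedule in Table 1 and the absence of a safeguard in section 6.2.

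It would be wrong to infer that the whole mediation aim fails or that efficacy is in doubt. The other two Self-Determination scales have Month-6 values that allow a lagged analysis, and the primary treatment comparison does not use the HCCQ. Severity is minor: one scale in a secondary aim.

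**What to change.** 1. Add the HCCQ to the Month-6 survey, and reconcile Table 1 with the general statement in section 3.3 on repeat measurement.
2. State in section 6.2 that HCCQ mediation of the Month-12 outcome uses the Month-6 value, with an analysis that also adjusts for Month-6 restraint behaviour, which is already collected. Earlier timing alone is not enough. Show adjusted and unadjusted results together: Month-6 behaviour is itself post-randomisation, so adjustment would also remove any genuine mediation that had already acted on behaviour by then.
3. State that a Month-6 mediator reflects the basic intervention only and cannot carry any effect of the enhanced component. Keep the Month-12 values of the other two scales for that question.
4. If Month 6 has passed, do not test the HCCQ as a mediator. Report it as a 12-month outcome or a cross-sectional association.

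The cost is one scale added to a survey already given, making it slightly longer, and a few sentences in section 6.2. The fallback in item 4 needs no new data.
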